8. ASSESSMENT OF SAFETY AND TOLERABILITY

8.1 Safety and Tolerability

Neurotidine®, used in the present study, is a Citicoline-based food supplement. The tolerability of Citicoline by the human body is well known since it is an endogenous substance, and has so far been administered intravenously, intramuscularly, orally and topically (26). No adverse events attributable to the administration of such Citicoline-based supplement have been reported to date.

The only warnings are not to take Neurotidine® during pregnancy and lactation, as the possible effects on the fetus and/or newborn are not fully known.

For this reason, pregnant or breast-feeding women cannot participate in the study; at the same time, women of childbearing age must agree to the use of adequate contraception methods throughout the duration of treatment with Citicoline envisaged by the study; for the safety of patients it should be emphasised that scientifically accepted birth control methods do not provide absolute protection: some women have become pregnant even with the regular use of these types of methods. However, despite our experience and that of others (19, 23, 25, 30, 31, 37, 40) leading us to assume that no patient should suffer adverse events, throughout the duration of the study, particular attention will be paid to patients' descriptions of their general conditions (e.g. increase/decrease in systemic blood pressure, gastric pyrosis, skin rashes, etc.) The safety and tolerability of the food supplement will be evaluated at the end of the study, analysing all the information collected.

All this information will be recorded on the appropriate CRF, at the times and in the manner described in the dedicated sections of this protocol.

8.2 Incidents or Near-Incidents

Clinical tolerability to treatment will be assessed by recording the occurrence of incidents or near-Incidents reported by the Patient or observed by the Investigator. This registration will be made from the moment the patient signs the informed consent.

All Incidents occurring during the clinical trial must be reported on the CRF.

8.2.1 Definitions

a) Incident

Also taking into account the European guideline on vigilance "incident" means the condition in which any malfunction or deterioration in the characteristics and/or performance, as well as any inadequacy in the labelling or the instructions for use of a food supplement has led, directly or indirectly, to the death of a patient or user or to a serious deterioration in their state of health. Serious deterioration of state of health means: a life-threatening illness or injury; an impairment of a bodily function or injury to a body structure; a condition that requires medical or surgical intervention to

prevent an impairment of a bodily function or injury to a body structure; a condition that causes hospitalization or the extension of hospitalization.

b) Near-Incident

A near-incident means: (a) the condition in which any malfunction or deterioration in the characteristics or performance, as well as any inadequacy in the labelling or instructions for use of a food supplement, could have caused, directly or indirectly, if the food supplement had been used, a serious deterioration of the state of health or death of the patient or user;

(b) the condition in which any malfunction or deterioration in the characteristics or performance, as well as any inadequacy in the labelling or instructions for use of a food supplement, could have caused, during use or as a result of use, a serious deterioration in the state of health or death of the patient or a user, had the health care professional not intervened.

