8.2.2 Incident or near-incident reporting

Investigators involved in the clinical trial are required to complete the standard section for gathering information on Incidents or near-Incidents in the CRF of the study.

a) Methods of communicating the Incident or Near-Incident

Upon the occurrence of an incident or near-incident, the Investigator must complete the CRF page for reporting all Incidents and near-incidents and the appropriate form (Incident or near-incident report by health care professionals to the Ministry of Health) relative to the reporting of Incidents caused by taking food supplements.

This Form, accompanied by a duly compiled submission form, must be sent by [contact]) within 24 hours of knowledge of the incident to the Hospital Department of Visual Neurophysiology and Neurophthalmology, Bietti-IRCCS Foundation, which will directly inform the persons responsible for monitoring medical devices of the Ministry of Health.

b) Further Investigations

The Investigator and the other persons responsible for Patient health must conduct any further investigation of Incidents or Near-Incidents, based on their clinical judgement of the likely causal factors.

c) Regulatory aspects

The Bietti-IRCCS Foundation is responsible for reporting to the competent Health Authorities any information relating to the safety of its medications. It is therefore essential for the Investigator to promptly report any Incident or Near-Incident, in order to allow it to comply with such requirements. These responsibilities are accepted by the Investigator as per the conditions set out in this protocol.

d) Instructions for Compiling the Forms Provided

For the compilation of the CRF page as well as the incident or near-incident report by health care professionals to the Ministry of Health, the Investigator should refer to the instructions provided to him/her together with such forms.

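### Section 8.1 promises to record and evaluate ordinary symptoms, but the tolerability measure set in 8.2 and 8.2.1 excludes them by definition

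*Protocol*

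**What the plan says.** Section 8.1 draws attention to what patients report about their general condition and gives examples: "increase/decrease in systemic blood pressure, gastric pyrosis, skin rashes". It then commits to an analysis: "The safety and tolerability of the food supplement will be evaluated at the end of the study", drawing on everything collected. It leaves the method of recording to other parts of the protocol: "All this information will be recorded on the appropriate CRF, at the times and in the manner described in the dedicated sections of this protocol".

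The sections that follow are 8.2 to 8.2.3. Section 8.2 names the measure: "Clinical tolerability to treatment will be assessed by recording the occurrence of incidents or near-Incidents". On timing it adds: "This registration will be made from the moment the patient signs the informed consent".

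Section 8.2.1 defines an incident through its cause, "any malfunction or deterioration in the characteristics and/or performance, as well as any inadequacy in the labelling or the instructions for use", and requires that this led to death or serious deterioration of health. A near-incident needs the same kind of cause and a potential for harm. In its first form the fault "could have caused, directly or indirectly, if the food supplement had been used, a serious deterioration of the state of health" or death; in its second form serious harm would have followed had a health professional not stepped in.

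Section 8.2.2 describes a CRF section for these two categories only. It refers to a Ministry form "relative to the reporting of Incidents caused by taking food supplements". It also makes the sponsor answerable to the authorities for any safety information.

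**The concern.** Section 8.1 gives investigators a duty and sends them elsewhere for the times and the manner. The place they are sent to uses a device-vigilance definition that does not fit the events 8.1 has in mind. An investigator who applies 8.2.1 as written would not enter heartburn or a rash after a properly made and labelled bottle as an incident, and no other page is specified for it.

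What is at stake is the safety and tolerability evaluation. Section 8.1 already expects that no patient will suffer adverse events. If the measure named in 8.2 returned zero in both arms, that would look like confirmation, although the definition would give the same result whatever the frequency of ordinary reactions.

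**Working it through.** No arithmetic applies, and the protocol gives no figure to reproduce. The check is to apply the definitions to the protocol's own examples, and then to look for any other route that would capture them.

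**Step 1: the two conditions in 8.2.1.** Both terms need (a) a fault in the product, its labelling or its instructions, and (b) death or serious deterioration of health, actual for an incident and potential for a near-incident.

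**Step 2: apply them.**

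| Event with a sound, correctly labelled product | (a) fault | (b) serious harm | Counted under 8.2 |
|---|---|---|---|
| Gastric pyrosis | no | usually no | no |
| Skin rash | no | usually no | no |
| Blood-pressure change | no | usually no | no |
| Serious reaction, for example with hospital admission | no | yes | no |

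Condition (a) fails in every row. The list of serious harms in 8.2.1 includes impairment of a bodily function without further qualification, so (b) could be read broadly, but that does not help while (a) is unmet.

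**Step 3: other routes.**

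| Place | What it can pick up | Named as a tolerability record |
|---|---|---|
| 5.2, Concomitant diseases row (T0, T1, T2, T3) | new illness at any visit | no |
| 7.7 | medication needed for new symptoms | no |
| 7.8 | new or changed therapies | no |
| 7.11 | discontinuations, with 30 days of follow-up | no |
| 8.2.3 | overdose, including without an incident | no |

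An untreated rash in a patient who continues might appear under Concomitant diseases, but nothing directs the investigator to put it there or links that row to 8.1.

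**Step 4: reporting to the sponsor.** Section 8.2.2 makes the sponsor responsible for any safety information but asks investigators only for incidents and near-incidents. Apart from overdose in 8.2.3, a serious reaction without a product fault has no stated route to the sponsor.

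**Step 5: timing, a minor note.** Section 8.2 starts registration at consent, which is T0. The 5.2 table ticks Incidents at T2 and T3 only, that is 2 of 4 visits. Under 5.4, product is handed over at the end of T1, so the untidy part is the 7 to 15 days between T0 and T1, before dosing.

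**The case against.** The strongest reply is that 8.1 itself requires these symptoms to go on the CRF and bases the evaluation on all information collected, while 8.2 does not say that incidents are the only source. The CRF is not at hand and may contain a symptom page. Concomitant diseases are collected at every visit in both arms. This stands in part. A reader might infer that ordinary symptoms will go unrecorded, or that the evaluation will rest on the 8.2 count alone; the protocol supports neither. What remains is that 8.1 refers to dedicated sections, and those sections define, record and schedule something else.

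A second reply is that the word incident was meant broadly. The Ministry form in 8.2.2 is described in terms of incidents caused by taking supplements, and 7.11 mentions incidents without speaking of a fault. This suggests loose usage, but only the narrow meaning is defined. Nor should it be pushed the other way: a reader might take 7.11 as a second, contradictory definition, but it is merely silent on cause, and an 8.2.1 incident fits its sentence.

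A third tempting inference is that the missing tick at T1 loses data on treatment. It does not. T1 precedes dosing, T2 and T3 are all the scheduled visits on treatment, and registration under 8.2 depends on patient report or investigator observation rather than on a visit.

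**Conclusion.** The point holds as a conflict between 8.1 on one side and 8.2 with 8.2.1 on the other. The tolerability measure that the protocol names excludes all three of its own examples, and serious reactions as well, whenever the product and its labelling are sound. A zero under 8.2 would therefore say little about tolerability over 12 months. This is a rule that the protocol states, not a detail left to an analysis plan.

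The conclusion rests on reading 8.2.1 as written. It does not depend on any assumed event rate. How many reactions would be missed cannot be estimated from the protocol, because the secondary routes may catch some of them. The efficacy analysis is unaffected. The text should be corrected, because without that the arms cannot be compared systematically on ordinary reactions.

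**What to change.** - **Define adverse event in section 8:** any untoward medical occurrence, serious or not and related or not, from consent to the last visit or the end of the 30-day follow-up in 7.11, whichever is later.
- **Make it the tolerability measure in 8.2**, and name that section in 8.1 in place of the general reference.
- **Record it on a CRF page at the existing visits**, and summarise it by arm in the evaluation that 8.1 promises.
- **Add an adverse-event row to the 5.2 table and keep the Incidents row.** Renaming the existing row would remove the incident check. Align the ticks with registration from consent.
- **Keep incident and near-incident as the vigilance category, and reconcile 8.2.2** so that serious reactions without a product fault also reach the sponsor.

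No rule for stopping treatment is proposed. The cost is wording in 8.1, 8.2, 8.2.1 and 8.2.2, one schedule row, one CRF page, and a little more data entry at visits that take place anyway.

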8.2.2 Incident or near-incident reporting

Investigators involved in the clinical trial are required to complete the standard section for gathering information on Incidents or near-Incidents in the CRF of the study.

a) Methods of communicating the Incident or Near-Incident

Upon the occurrence of an incident or near-incident, the Investigator must complete the CRF page for reporting all Incidents and near-incidents and the appropriate form (Incident or near-incident report by health care professionals to the Ministry of Health) relative to the reporting of Incidents caused by taking food supplements.

This Form, accompanied by a duly compiled submission form, must be sent by [contact]) within 24 hours of knowledge of the incident to the Hospital Department of Visual Neurophysiology and Neurophthalmology, Bietti-IRCCS Foundation, which will directly inform the persons responsible for monitoring medical devices of the Ministry of Health.

b) Further Investigations

The Investigator and the other persons responsible for Patient health must conduct any further investigation of Incidents or Near-Incidents, based on their clinical judgement of the likely causal factors.

c) Regulatory aspects

The Bietti-IRCCS Foundation is responsible for reporting to the competent Health Authorities any information relating to the safety of its medications. It is therefore essential for the Investigator to promptly report any Incident or Near-Incident, in order to allow it to comply with such requirements. These responsibilities are accepted by the Investigator as per the conditions set out in this protocol.

d) Instructions for Compiling the Forms Provided

For the compilation of the CRF page as well as the incident or near-incident report by health care professionals to the Ministry of Health, the Investigator should refer to the instructions provided to him/her together with such forms.

8.2.3 Overdose

Cases of overdose (accidental or intentional) leading to Incidents or near- incidents should be managed according to emergency procedures. This includes reports of food supplement intake for suicidal purposes with consequent overdose of such food supplement. Reports of overdose not associated with incidents should also be reported to the **Hospital Department of Visual Neurophysiology and Neurophthalmology, Bietti-IRCCS Foundation**, (although not requiring notification to Regulatory Authorities), in order to obtain information on symptoms, corrective treatment and the outcome of such an overdose.

9. STATISTICAL ANALYSIS

9.1 Sample size

As already highlighted, the main measure on which we relied for the calculation of the sample size is the RCT.

Our aim is to evaluate the value of the RCT parameter in the group treated with Neurotidine®, compared to that of the group treated with placebo.

We consider the following RCT values: at baseline 70.21 ± 9.12 ms and at the end of treatment 63.3 ± 8.15 ms (19), with an α error of 5% and a power of 80%.

We obtain 27 participants to which we add a drop-out equal to 10%, so the final value is 30 for each group.

9.2 General methodology

The data of each group, obtained from the PEV, PERG, CV, OCT and RM measurements will be represented by their mean and standard deviation, after having verified their normal distribution by means of the Anderson-Darling and Kolmogorov-Smirnov tests.

For each group, any variations in the measurements indicated above will be evaluated by means of a t-test for paired data.

Furthermore, the parameters of the electrophysiological, morphological and MRI measurements related to the two groups will be compared pre and post treatment, by means of ANOVA with correction of multiple comparisons based on Tukey's method.

The functional electrophysiological parameters (PEV and PERG) will be correlated by Pearson's test with the morphological OCT ones.

Finally, the possible relationship between the PEV, PERG and functional RM parameters of connection of the networks will be assessed using Pearson's test.

This analysis will be repeated respectively between the PEV and PERG parameters and the RM parameters in diffusion for each area indicated in paragraph 5.6.

The p-value of less than 5% is considered significant for any previously exposed test.

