2. OBJECTIVES AND AIMS OF THE STUDY

- 1) Primary Objective: to evaluate whether treatment with **Citicoline in oral solution** can produce an improvement of the post-retinal nerve conduction, altered base in patients with OAG.
- 2) Secondary objective: to evaluate in patients with OAG whether the possible changes in post-retinal nerve conduction induced by treatment with Citicoline in oral solution (information obtained through electrophysiological recordings) are associated or not with **morphological and functional variations of the nervous structures that form the optical pathways** (NGL, optic tract, visual cortex, information obtained through the acquisition of structural and functional magnetic resonance imaging) and whether both conditions can be related to the morpho-functional variations of the RGCs and of the visual field (CV).

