5.5 Outcomes

The nerve conduction along the post-retinal optical pathways will be determined through the evaluation of the RCT through the simultaneous recording of PERG and PEV, the function of the RGCs will be evaluated through the recording of the PERG, the morphological evaluation of the RGCs will be carried out through the OCT evaluations and the morphological and functional evaluation of the nerve structures that form the optical pathways will be performed by means of Cerebral Magnetic Resonance (MRI).

The primary objective is the assessment of changes in the RCT in patients treated with citicoline in oral solution compared to changes in the RCT assessed in patients treated with placebo.

The secondary objectives will be to evaluate whether the changes in RCT in patients treated with Citicoline in oral solution are associated or not with **morphological and functional changes in the nerve structures that form the optical pathways** (NGL, optic tract, visual cortex) and if both conditions may be related to the morpho-functional variations of the RGCs and of the visual field.

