10. EXPECTED RESULTS AND NEUROFUNCTIONAL CONSIDERATIONS

10.1 Expected results and their impact in clinical practice.

As for the primary objective, the expected result is that Citicoline in oral solution can improve post-retinal nerve conduction.

As regards the **secondary objectives**, the expected result consists in the possibility of detecting that any improvements in post-retinal nerve conduction after treatment with Citicoline in oral solution may or may not be associated with changes in the structure and function of the nerve stations that form the pathways. optical (assessed by MRI) depending on or independently of the morpho-functional condition of the RGCs and of the CV.

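### Section 9.2 does not tie the primary RCT objective to one between-arm contrast, and a baseline-adjusted comparison would settle this and gain precision at no cost

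*Protocol*

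**What the plan says.** The question is stated in four places, not all in the same way.

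- Section 5.5 sets the primary objective as RCT changes on citicoline "compared to changes in the RCT assessed in patients treated with placebo".
- Section 9.1 gives the aim as the RCT value on the active product "compared to that of the group treated with placebo".
- Section 2 asks whether citicoline "can produce an improvement of the post-retinal nerve conduction" and names no comparator.
- Section 10.1 likewise: "the expected result is that Citicoline in oral solution can improve post-retinal nerve conduction".

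The tests are in section 9.2.

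- Within arms: "For each group, any variations in the measurements indicated above will be evaluated by means of a t-test for paired data".
- Between arms: the electrophysiological, morphological and MRI parameters "related to the two groups will be compared pre and post treatment, by means of ANOVA with correction of multiple comparisons based on" Tukey's method.
- Threshold: "The p-value of less than 5% is considered significant for any previously exposed test".

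RCT is not named in 9.2. It falls under the electrophysiological parameters because 5.6 defines it as the P100 latency of the VEP minus the P50 latency of the PERG. No sentence ties the ANOVA, or any contrast within it, to the primary objective. The sample size inputs in 9.1 are RCT values "at baseline 70.21 ± 9.12 ms and at the end of treatment 63.3 ± 8.15 ms", which are a before-after pair. No placebo value is given.

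**The concern.** A placebo arm answers the primary question only if the between-arm contrast decides it. A paired test in one arm cannot separate a drug effect from drift or regression to the mean, and section 4.1 selects patients for a raised RCT. Section 9.2 puts the two kinds of test side by side at the same threshold. A significant fall in the citicoline arm could therefore be reported as the result expected in 10.1 even if the between-arm contrast shows nothing. That would contradict 5.5 but would not contradict 9.2.

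The between-arm method is also loosely specified. A pre/post ANOVA with Tukey correction could mean a comparison at T3, a comparison of changes, or all pairs of arm-by-time cells. Two arms at two times give 4 cells and 4 × 3 / 2 = 6 pairs, of which only one or two bear on the objective. RCT is recorded at T1 in every patient, and the plan does not use it as a covariate, which is where precision is lost.

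**Working it through.** **Inputs.** From 9.1: RCT 70.21 (SD 9.12) ms at baseline and 63.3 (SD 8.15) ms at end of treatment, α 5%, power 80%, 27 per group, 30 after drop-out. Assumed: two-sided testing, 27 completers per arm, 6.91 ms taken as the between-arm difference, and pre-post correlation r = 0.3 / 0.5 / 0.7, because the protocol gives none.

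**1. The plan's own figure.** Difference = 70.21 − 63.3 = 6.91 ms. Pooled SD = √[(9.12² + 8.15²)/2] = 8.649 ms.
- Two-sample formula, n = 2·SD²·(1.960 + 0.842)²/6.91²: 24.6, so 25 per arm with the pooled SD; 27.3, so 28 with SD 9.12. Solving with the t distribution gives 26 and 29.
- Paired t-test at r = 0: SD of change = √(9.12² + 8.15²) = 12.23 ms, n = 26.6, so 27. At r = 0.5 the paired test would need only 14.4, so 15.

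The stated 27 fits either route, so the sample size does not show which test was meant.

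**2. Smallest significant results.** SD of change = √(9.12² + 8.15² − 2·r·9.12·8.15). Paired threshold = 2.056·SD/√27. Between-arm threshold for change = 2.007·SD·√(2/27).

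| r | SD of change (ms) | Paired, citicoline arm (ms) | Between-arm difference in change (ms) |
|---|---|---|---|
| 0.3 | 10.25 | 4.05 | 5.60 |
| 0.5 | 8.68 | 3.43 | 4.74 |
| 0.7 | 6.75 | 2.67 | 3.69 |

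A citicoline fall of 4 ms at r = 0.5 would pass the paired test. A difference of 4 ms from placebo would not pass the between-arm test.

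**3. Null trials, no drift.** Count as success a favourable citicoline paired test or a favourable between-arm test of change. In 200,000 simulated trials per value of r, about 4.2% are favourable. The between-arm test alone gives 2.5%.

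**4. Null trials with drift (illustration only).** If RCT fell by 2 ms in both arms, the citicoline paired test would be favourable in 16 / 21 / 32% of trials. If it rose by 1 ms in both arms, the figure is 0.7% or less. The between-arm test stays at 2.5%. The protocol gives no drift in either direction.

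**5. Power for a 6.91 ms between-arm difference, 27 per arm.**
- Unadjusted at T3: SD 8.649, 52 df.
- Change scores: SD of change from step 2, 52 df.
- ANCOVA on T1 RCT: SD = 8.649·√(1 − r²) = 8.25 / 7.49 / 6.18 ms, 51 df.

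| r | Unadjusted at T3 | Change scores | ANCOVA |
|---|---|---|---|
| 0.3 | 82% | 68% | 86% |
| 0.5 | 82% | 82% | 91% |
| 0.7 | 82% | 96% | 98% |

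ANCOVA is the best of the three at every r. The gain over the unadjusted test is small at r = 0.3. Over change scores it is large at r = 0.3 and small at r = 0.7.

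**The case against.** The strongest reply is that the protocol already answers the question. Sections 5.5 and 9.1 both state the comparison with placebo, and of the two RCT tests in 9.2 only the ANOVA can address it. The exact model and covariates are often left to a statistical analysis plan. Listing within-arm tests beside a between-arm test is not in itself an error. This stands, and it limits the point to an ambiguity plus an avoidable loss of precision. What remains is that the protocol sets out its own list of tests with one threshold for all, and states its own objective with and without the comparator.

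Three stronger readings are tempting, and the document does not support them.

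- *A within-arm test is the decision rule.* A 5% threshold for every test is not a success criterion. Sections 2 and 10.1 state an objective and an expectation, in wording that is ordinary for a placebo-controlled trial.
- *The trial was sized for a paired test.* The inputs are a before-after pair, but 27 agrees equally well with a two-sample calculation, and 9.1 sizes each group for a comparison with placebo.
- *The false-positive risk is known to be large.* Rates such as 16 to 32% need an assumed common fall. Entry on a raised RCT makes regression to the mean possible. However, section 6 places the criteria check at screening, and PERG and VEP are recorded afresh at T1, which may remove much of it. The inclusion/exclusion row of 5.2 is ticked at all four visits, so it does not show re-selection on RCT at T1.

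**Conclusion.** The point holds as an ambiguity with a free improvement attached; severity is minor to should-fix. Section 9.2 does not tie the objective of 5.5 to one between-arm contrast, and sections 2 and 10.1 omit the comparator.

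Without any drift assumption, the looseness is worth about 4.2% against 2.5% favourable null trials. The choice of between-arm method is worth 4 to 16 percentage points of power against an unadjusted comparison at T3 (86 − 82 to 98 − 82), and 18 to 2 points against change scores (86 − 68 to 98 − 96), as r goes from 0.3 to 0.7.

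These figures rest on the assumed r, on 6.91 ms as the between-arm difference, on 27 completers per arm, and on sound randomisation, which the 2.5% for the between-arm test also requires. An unadjusted between-arm test would be valid, so the adjustment improves precision and does not correct an error.

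**What to change.** In 9.2, name a single primary analysis: the citicoline minus placebo difference in RCT at T3, two-sided 5%, by ANCOVA adjusted for RCT at T1. State that no Tukey correction applies to this one contrast. Label the within-arm paired t-tests descriptive. Add the placebo comparison to the wording of sections 2 and 10.1 so that they agree with 5.5.

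The essential part is naming the between-arm contrast; the covariate adds the precision. The cost is a few sentences and a few lines of code. There is no change to sample size, visits or data, since T1 RCT is already collected. The only downside is that within-arm p-values can no longer be claimed as evidence of efficacy.
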